10.5.1 Missing data

Missing data is a potential major source of bias in HRQoL assessment.

In order to check the potential impact in the study, the compliance mechanism will be investigated prior to initiating the HRQoL analysis. Characteristics of patients with and without valid HRQoL data will be compared and trends over time per dropout pattern will be investigated. Model building will be used in order to investigate whether the compliance mechanism is linked to selected prognostic variables.

Once the main analysis is completed, sensitivity analyses will be undertaken to verify the robustness of the results vis-à-vis the missing data.

In case overall compliance is deemed too low (<50%), only an exploratory analysis will be performed in lieu of the main analysis.

10.5.2 Other exploratory analyses

The HRQoL scales from the QLQ-C30 and QLQ-LC13 not included as key or supportive exploratory endpoints will be analyzed as "other" exploratory endpoints. The financial difficulties scale will be excluded completely from analysis.

An exploratory analysis of the difference in HRQoL score for progressed patients compared to patients with no radiographic evidence of tumor progression will be subject to compliance and data availability. The aim is to estimate the amount and nature of deterioration in

HRQoL that is associated with disease progression. The change from baseline per HRQoL scale to (i) the most recent HRQoL assessment before progression and (ii) the most recent HRQoL assessment after progression will be calculated and classified based on clinical relevance. A difference of ≥ 10 points on the 100 point linearly-transformed scale will be considered clinically relevant. Additionally, a longitudinal data analysis model can be constructed, with the HRQoL score as dependent variable, and treatment, time, selected clinical factors, and progression status (time-varying) as independent covariates.

10.6 EQ-5D instrument

The EQ-5D is a general health status and health utility measure [Ref. 64]. It measures 5 dimensions of health state: mobility, self-care, usual activities, pain/discomfort, and anxiety/depression each assessed by a single question on a three-point ordinal scale. It also includes a VAS scale to measure health state. The EQ-5D will be included in this study for the purpose of the computation of utilities that can be used in health economic studies. This instrument has been used extensively in cancer studies and published results from these studies support its validity and reliability [Ref. 65]. In addition, validated translations for this instrument are available for a number of countries and languages (Appendix E).

The assessment schedule of the EQ-5D is identical to the schedule of the HRQoL instrument (QLQ-C30) as described in Section 10.4.1.

11 Translational research

PD-L1 IHC expression was described in many histological cancer types, particularly in melanoma and lung cancer. In NSCLC the expression pattern is variable among the different reports ranging from 36 to 50%, according to histologic subtype [Ref. 47, Ref. 48, Ref. 54]. PD-L1 IHC positive tumors showed higher response rates than those with no expression (36 versus 13%) [Ref. 56], with a significant degree of variability according to the testing method as well as positivity definition and threshold used across the various clinical trials.

Data available so far are mainly in the advanced setting but Azuma and colleagues have recently published the results of their study on the PD-L1 expression in 164 surgically resected NSCLC. In that series, the expression of PD-L1 was significantly higher for women than for men, for never-smokers than for smokers, and for patients with adenocarcinoma rather than for those with squamous cell carcinoma. The multivariate analysis revealed that the presence of EGFR mutation and adenocarcinoma histology were significantly associated with increased PD-L1 status [Ref. 80]. These data need to be confirmed and prospectively evaluated; heterogeneity in early stage disease needs to be further explored.

PD-L1 status has been correlated with EGFR and RAS mutations and to date the results show no clear trend, largely because of the lack of standardization of the PDL1 definition of positivity, and lack of comparison between antibody use and companion diagnostics.

11.1 Objectives

[figure not shown]
The aim of this translational part of PEARLS is to explore the immunological parameters that parallel tumor recurrence over time (including new second primaries), in patients treated by pembrolizumab in comparison to the placebo arm. Finally data extracted would help identifying a potential set of prognostic or predictive markers for immune checkpoint inhibitors such as anti PD1 blockers.

[figure not shown]
Exploratory parameters in this study will be refined according to the current knowledge in the field during trial advancement and at the time of trial completion.

A preliminary proposal of the main objectives of the TR project could focus – based on the current available knowledge in the field and subject to changes accordingly - at least (i.e. not limited to) on analyzing:

PPD

11.2 Summary of sample collection

This exploratory translational program would require the collection of the following material:

Table 11. Sample collection

Specimen type(s)	Specimen amount	Collection time point(s)	Storage conditions	Estimated sample size
Tumor tissue	FFPE Block (highly preferred) or slides 20-25	At surgery	Blocks: Room temperature (RT) if outdoor temperature is < 24°C/75°F, refrigerated if RT > 24°C/75°F Slides: refrigerated 2°C-8°C	1180, after central PD-L1 testing for stratification
Tumor tissue	Fresh frozen upon feasibility results for those sites able to collect it (as standard practice) at the time of surgery	At surgery	Fresh frozen: As per local standard practice	Selected centers 50-100 samples randomly distributed between the 2 treatment arms
Tumor tissue	FFPE Block (highly preferred) or slides 20-25	Biopsy at relapse (optional)	Blocks: Room temperature (RT) if outdoor temperature is < 24°C/75°F, refrigerated if RT > 24°C/75°F Slides: refrigerated 2°C-8°C	Selected patients across all participating centers upon patients consent 150-200 samples
Serum	20 mL	At enrollment step 1	Store at -70°C/-80°C freezer	1180 patients

Specimen type(s)	Specimen amount	Collection time point(s)	Storage conditions	Estimated sample size
Whole blood (germline source)	20mL	At enrollment step 1	Tubes MUST be in -20°C freezer for 24 hrs Transfer to -70°C/-80°C freezer	1180 patients
Serum	20 mL	At enrollment step 3, if adjuvant chemotherapy was delivered only	Store at -70°C/-80°C freezer	Btw 65-80% of the 1180 patients
Serum	10 mL	At week 12 since D 1 infusion 1 – with first CT scan post randomization	Store at -70°C/-80°C freezer	1180 patients
Serum	10 mL	At completion or discontinuation of treatment	Store at -70°C/-80°C freezer	1180 patients
Serum	20 mL	At relapse	Store at -70°C/-80°C freezer	Expected approx. 50% of patients
PBMC	Up to 40 mL	
 ◆ Before treatment start ◆ At week 12 since D 1 infusion 1 ◆ At tumor relapse 	Frozen at -70°C/-80°C (max. 21 days) >21 days, store in liquid nitrogen tank. Shipment must be maintained in liquid nitrogen	In selected centers (Switzerland, Spain, France)
Whole Blood for correlative study (DNA)	8.5 mL	Before treatment start (step 3)	Place in -20°C freezer for 24 hrs Transfer to -70°C or colder for at least 24 hrs before shipping	1180 patients

Specimen type(s)	Specimen amount	Collection time point(s)	Storage conditions	Estimated sample size
Whole Blood for correlative study (RNA)	2.5 mL	Before treatment start (step 3) At week 12 since D 1 infusion 1 At completion or discontinuation	Place in -20°C freezer for 24 hrs Transfer to -70°C/-80°C or colder until ready to ship	1180 patients

11.3 Statistical considerations

The primary outcome is tumor recurrence over time (including new second primaries). Tumor and serum samples are collected according to Section 11.2.

The sample size of 1180 patients gives adequate power to detect realistic prognostic effects for immunological parameters on the outcome of interest. More specifically, with 1180 patients available, we will be able to observe 551 tumor recurrences (see also Chapter 8). Assuming that expression of each particular immunological marker will be present in 25-75% of the available sample, the study will be adequately powered (over 80% power) for detecting a targeted HR of 0.78 or less, using a two-sided significance level of 5%. For serial measurements available for about 75% of the total sample of patients, a targeted HR of 0.75 or less can be detected with over 80% power.

Table 12. Maximum detectable HR with around 80% power under different scenarios for the immunological marker incidence.

Marker incidence	Detected HR	alpha	Power
25%	0.78	5%	80%
50%	0.78	5%	80%
75%	0.78	5%	80%
25%	0.75	5%	81%
50%	0.75	5%	81%
75%	0.75	5%	81%

For the analyses exploring the predictive ability of immunological parameters, the critical values will result from procedures to control the false discovery rate (FDR) [Ref. 81, Ref. 82]. When applied to censored failure time outcomes, this approach assumes that censoring is not related to the variables being analyzed. Whether censoring can be considered as random, will be examined during the analysis.

In order to determine the significance of candidate prognostic / predictive markers, we will use Cox model score tests as an initially screening procedure and then apply LASSO as a selection procedure for the markers. Note that we will also evaluate the correlation structure

of the markers. If the correlations are large then we may switch to a procedure more appropriate like the OSCAR [Ref. 83].

A permutation approach [Ref. 82] will be used to control the false discovery rate in the set of variables selected. The initial modeling may only consider the most promising variables based on univariate analyses (all variables will be checked again relative to the final model).

Cross-validated partial likelihood approach (10-fold or 20-fold depending on total sample size) will be used to test the results and the predictability of the derived Cox model. This will be an internal validation of the approach.

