	
 ◆ A Hwang-Shih-DeCani (HSD) spending function with $\gamma = -4$ is used to establish the boundary (nominal α) in interim and final analysis of DFS and OS for the test of each population. The threshold αs and HRs for each analysis can be found in Table 8 and Table 9 in Section 8.1.1. ◆ The timing of interim analysis 1 and 2 will be determined by the number of DFS events in the PD-L1 strong positive population, and the final analysis for DFS will be conducted when target DFS event numbers are reached in the whole population as well as the PD-L1 strong positive subgroup. 
Approximately 1180 participants will be randomized in a 1:1 ratio into the experimental arm and the control arm. For DFS, based on a target number of 551 events at FA, the study has ~86% power at $\alpha=1.25\%$ (one-sided) and ~92% power at $\alpha=2.5\%$ (one-sided) for the whole population. It is expected that there will be approximately 334 participants of PD-L1 strong positive in the study to achieve ~90% power at final analysis of DFS at $\alpha=1.25\%$ (one-sided) and ~94% power at $\alpha=2.5\%$ (one-sided). If either of the tests for the primary endpoints is significant, then the study can be declared successful in the respective population.

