7.1.2 Disease free survival (DFS)

Definition of date of disease recurrence is given above (see [Section 7.1.1.3](#)). Recurrence of disease can be a loco-regional recurrence, a distant (metastatic) recurrence or a second primary. NSCLC and second malignancies will be considered to be events.

Disease Free Survival (DFS) is calculated as the time from randomization to either the date of disease recurrence or the date of death (whatever the cause). The date of first documented disease recurrence (if applicable) will be used as the date of event. Patients alive with no evidence of disease recurrence at the time of their last visit are censored at the time of the last examination.

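### Section 11.3 claims over 80% power for any marker present in 25–75% of patients, but 551 events and HR 0.78 give about 71% at 25% or 75% incidence

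*Combined protocol and SAP*

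**What the plan says.** Section 11.3 (Translational research, Statistical considerations) bases its power statement on 1180 patients, from whom "we will be able to observe 551 tumor recurrences". The claim is made for a marker "present in 25-75% of the available sample, the study will be adequately powered (over 80% power) for detecting a targeted HR of 0.78". Stronger effects are covered too, and the test is described as "using a two-sided significance level of 5" per cent. A second claim concerns repeated samples: "For serial measurements available for about 75% of the total sample of patients, a targeted HR of 0.75 or less can be detected", again with over 80% power.

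Table 12 is titled "Maximum detectable HR with around 80% power under different scenarios for the immunological marker incidence". It has six rows: HR 0.78 at 25%, 50% and 75% incidence, each with 80% power, and HR 0.75 at the same three incidences, each with 81%. Alpha is given as 5%, without sidedness. The table gives no event counts and does not say which rows belong to the serial-measurement scenario.

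The 551 comes from the DFS design: the Protocol summary gives whole-population DFS power "based on a target number of 551 events at FA". Section 7.1.2 runs DFS to "either the date of disease recurrence or the date of death (whatever the cause").

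**The concern.** When marker-positive patients are compared with marker-negative patients, the information in a fixed number of events is proportional to p(1−p), where p is the marker incidence. That is 0.25 at 50% incidence and 0.1875 at 25% or 75%, a quarter less. With events, hazard ratio and alpha held fixed, power must fall towards the ends of the range. A table that prints the same power at all three incidences cannot be right in every row, and the text's claim of over 80% across the whole range is least secure at 25% and 75%.

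What is at stake is the credibility of the stated power for the biomarker work. Section 11.4 says an analysis plan will be written for each translational project, and those plans could take their power figures from this table.

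**Working it through.** **Inputs.** From Section 11.3: d = 551 events; HR 0.78 (full sample) and 0.75 (serial samples); incidence p = 0.25, 0.50, 0.75; two-sided 5% (z = 1.960). The section names Cox score tests for marker screening. For a binary marker this is the log-rank test, so Schoenfeld's formula applies:

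power = Φ( √(d·p·(1−p)) × |ln HR| − z )

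**HR 0.78, 551 events, two-sided 5%** (|ln 0.78| = 0.2485)

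- p = 0.25 or 0.75: √(551 × 0.1875) = 10.164; 10.164 × 0.2485 − 1.960 = 0.565; power **71.4%** (Table 12: 80%).
- p = 0.50: √(551 × 0.25) = 11.737; 11.737 × 0.2485 − 1.960 = 0.956; power **83.0%** (Table 12: 80%).

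**Incidence range with at least 80% power.** This requires p(1−p) ≥ (1.960 + 0.842)² / (551 × 0.2485²) = 0.2307, so p runs from 0.361 to 0.639. At 25% or 75% incidence, 80% power needs 679 events; at 50% it needs 509.

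**HR 0.75 rows** (|ln 0.75| = 0.2877). Section 11.3 gives no event count. Two readings:

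| Events | 25% | 50% | 75% | Table 12 |
|---|---|---|---|---|
| 413 (0.75 × 551, assuming events scale with patients) | 71.6% | 83.2% | 71.6% | 81% |
| 551 (all) | 83.3% | 92.2% | 83.3% | 81% |

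Neither reading gives a constant 81%.

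**Detectable HR at 80% power**, exp(−2.802 / √(d·p·(1−p))): with 551 events, 0.76 at 25% or 75% and 0.79 at 50%; with 413 events, 0.73 and 0.76.

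**Other methods, HR 0.78, 551 events, two-sided 5%**

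| Method | 25% | 50% | 75% |
|---|---|---|---|
| Schoenfeld | 71.4% | 83.0% | 71.4% |
| Freedman, unequal groups | 65.8% | 82.7% | 76.4% |
| Log-rank simulation (1180 patients, exponential times, stopped at event 551, 20,000 runs) | 69.0% | 82.9% | 74.1% |

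With the HR reversed (1/0.78), simulation gives 73.8% at 25% and 68.0% at 75%. No two-sided method reaches 80% at either end.

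**Could the printed figures be one-sided?** A one-sided 5% test gives 81.1% at 25% or 75% for HR 0.78 with 551 events, and 81.2% for HR 0.75 with 413. Those are close to the printed 80% and 81%, but the 50% rows would be about 90%, and the text says two-sided. The origin of the printed figures is not known.

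**Event count.** The 551 include deaths without recurrence, so recurrences could be fewer and power lower. In the other direction, Table 11 puts serum samples at relapse at "Expected approx. 50% of patients". Taking 0.5 × 1180 = 590 events, power for HR 0.78 at 25% or 75% is Φ(√(590 × 0.1875) × 0.2485 − 1.960) = 74%, still below 80%.

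**The case against.** The strongest points on the other side are these.

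- **Table 12 says around 80%, not over 80%, and gives no sidedness.** This is true, and the over-80% and two-sided wording belongs to the text alone. But 71% is not around 80%, and the flat rows remain wrong.
- **The 36–64% limits are a formula approximation.** This stands in part. Simulation gives 78.5% at 36% and 81.9% at 64%. A variant with 52-month uniform entry and a 42-month control median (8,000 runs per point) puts the range at roughly 39–67%. The limits are approximate; the shortfall at 25% and 75% is not in doubt.
- **The HR 0.75 rows rest on an assumed 413 events.** This stands. With all 551 events those rows exceed 80%. What is firm is that the basis is unlabelled and that 81% cannot hold at all three incidences.
- **A single 5% test is not the planned procedure.** Section 11.3 also plans false discovery rate control and LASSO selection, so neither 71% nor 80% describes the power of the final analysis. But the section makes its power claim for a 5% test, and false discovery rate control would generally lower per-marker power further.
- **The work is exploratory.** This is agreed, and it limits the severity rather than removing the error.

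**Conclusion.** The concern holds. On the inputs printed in Section 11.3, power for HR 0.78 is about 71% at 25% or 75% incidence (66–76% across the methods tried) and about 83% at 50%. It reaches 80% only in the middle of the claimed range, about 36–64% by formula. At the ends, about 3 in 10 true effects of that size would be missed (1 − 0.714 = 0.286), against the 2 in 10 implied. Table 12's constant 80% and 81% cannot be right on any single basis.

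The HR 0.78 result needs no assumption beyond the section's own figures and a score or log-rank test of a binary marker. The HR 0.75 shortfall depends on the assumed 413 events. Calling the 551 tumor recurrences is a separate labelling error. Severity is minor: sample size, alpha and primary DFS power do not depend on this table.

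**What to change.** Recompute all six rows of Table 12 with one named method, state the sidedness and the event count for each row, and label the rows that refer to the serial-sample subset. Then bring the text of Section 11.3 into line. On the two-sided 5% basis, any one of these would do:

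- **Print the power.** By Schoenfeld: 71% / 83% / 71% for HR 0.78 with 551 events and, if 413 is confirmed as the serial-sample count, 72% / 83% / 72% for HR 0.75. Drop the over-80% claim for 25–75%.
- **Print the detectable HR at around 80% power.** By Schoenfeld: 0.76 / 0.79 / 0.76 with 551 events and 0.73 / 0.76 / 0.73 with 413. This fits the table's title.
- **Keep HR 0.78 and 0.75 and narrow the incidence range** to about 36–64%, or slightly narrower at the lower end to allow for the simulated shortfall there.

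In each case, call the 551 DFS events, or replace them with the expected number of recurrences and second primaries.

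The cost is a table and text correction in an exploratory section. The figures at 25% and 75% incidence become less favourable. No patients are added and the primary analysis does not change.

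### Section 11.3 quotes biomarker power for one prognostic marker at an unadjusted 5% level, which is not the power of the FDR-controlled selection procedure it plans

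*Combined protocol and SAP*

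**What the plan says.** The power statement in Section 11.3 concerns prognostic effects of immunological parameters. It takes the event count from the main trial ("with 1180 patients available, we will be able to observe 551 tumor recurrences"), assumes that each marker is present in 25-75% of the sample, and concludes that "the study will be adequately powered (over 80% power) for detecting a targeted HR of 0.78 or less, using a two-sided significance level of 5" per cent. For repeated samples it adds: "For serial measurements available for about 75% of the total sample of patients, a targeted HR of 0.75 or less can be detected", again with over 80% power. Table 12 lists HR 0.78 at 80% and HR 0.75 at 81%, each for incidences of 25%, 50% and 75%. Its alpha column reads 5% and gives no sidedness.

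The following paragraphs set the decision rule. For analyses of predictive ability, "the critical values will result from procedures to control the false discovery rate (FDR"). The significance of candidate prognostic and predictive markers alike is then determined by Cox score tests as a screen, followed by LASSO (or OSCAR if correlations are large). A permutation approach "will be used to control the false discovery rate in the set of variables selected". The section gives no FDR level, no number of markers and no power for this procedure. Section 11.4 leaves analytical detail to a separate plan for each translational project.

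**The concern.** Power belongs to a decision rule. Here it is computed for one rule (one marker, p below 5%) and the markers are declared by another (screening, penalised selection, FDR control across the candidate set). Under FDR control a marker with p = 0.03 will often not be declared, although it passes the alpha printed in Table 12. If the sentence stays as it is, a null biomarker result could be read as coming from an analysis with over 80% power when the analysis actually run may have had clearly less. The selection methods make sense only with several, possibly correlated, markers, so the multiplicity is intended.

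**Working it through.** **Inputs.** From Section 11.3: HR 0.78 with d = 551 events; HR 0.75 for serial measurements in about 75% of patients; incidence p = 25%, 50% or 75%; two-sided 5%. Assumption: events fall in proportion to patients, so d = 0.75 × 551 ≈ 413 for the serial case. The 551 is itself favourable. The protocol summary gives it as the DFS target ("based on a target number of 551 events at FA"), and DFS counts deaths as well as recurrences.

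**Step 1: the plan's own figure.** With z = ln(1/HR) × √(d·p·(1−p)), power at two-sided 5% is Φ(z − 1.960), and at one-sided 5% it is Φ(z − 1.645).

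| HR, events | Incidence | z | Two-sided 5% | One-sided 5% | Table 12 |
|---|---|---|---|---|---|
| 0.78, 551 | 25% or 75% | 2.525 | 71.4% | 81.1% | 80% |
| 0.78, 551 | 50% | 2.916 | 83.1% | 89.8% | 80% |
| 0.75, 413 | 25% or 75% | 2.532 | 71.7% | 81.3% | 81% |
| 0.75, 413 | 50% | 2.924 | 83.3% | 90.0% | 81% |

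No single sidedness reproduces the table. At the two-sided level stated in the text, the 50% rows meet the claim of over 80%, and the 25% and 75% rows miss it by about 8 to 9 points. Those four rows come close only at one-sided 5%.

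**Step 2: the two criteria.** The figures in Step 1 apply a cut-off of 5% to each marker. A step-up FDR procedure of the Benjamini-Hochberg type applies a cut-off of q·k/m, where q is the FDR level, m the number of markers and k the number declared. Since k ≤ m, the cut-off never exceeds q. With q at 5% or below, power for a given marker therefore cannot exceed the single-marker figure, whatever m is. With q above 5% the direction depends on how many markers are declared.

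**Step 3: illustrative size.** I simulated Benjamini-Hochberg on independent two-sided tests (20,000 replicates per cell; HR 0.78, 551 events; 10% of markers true). q, m and the true fraction are my assumptions. Average power per true marker, in per cent:

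| Incidence | q | m = 10 | m = 20 | m = 50 | m = 100 |
|---|---|---|---|---|---|
| 50% | 5% | 54.6 | 51.5 | 47.5 | 46.6 |
| 50% | 10% | 64.7 | 61.8 | 59.0 | 58.2 |
| 50% | 20% | 75.4 | 73.2 | 71.3 | 71.1 |
| 25% | 5% | 40.5 | 34.8 | 29.9 | 27.7 |
| 25% | 10% | 49.8 | 44.7 | 40.6 | 38.2 |
| 25% | 20% | 61.8 | 58.0 | 54.2 | 52.7 |

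HR 0.75 with 413 events gives nearly the same values, because z is nearly the same.

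**Step 4: settings that change the answer.** At 50% incidence, q = 20% with 20% true markers gives about 80-81%, q = 10% with half true about 81-82%, and q = 20% with half true about 90%. In the other direction, q = 5% with one true marker among 100 gives 29%.

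**The case against.** The strongest defence is that single-marker power at a printed alpha is an ordinary planning figure. The work is exploratory, the 1180 patients come from the DFS design, and Section 11.4 requires an approved analysis plan for each project. No trial decision rests on Table 12. That limits the importance of the point. It does not correct a protocol sentence that already asserts adequate power while the same section has already chosen FDR control.

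The power sentence is about prognostic effects, and the first FDR sentence covers predictive analyses only. That is correct, and the mismatch should not be rested on that sentence. It rests on the later text, which names prognostic and predictive markers together and controls FDR in the selected set.

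Benjamini-Hochberg on independent tests is not the planned sequence of screening, LASSO and permutation. This also stands, so the figures in Step 3 illustrate and do not replace. In addition, the list of objectives in Section 11.1 is blacked out, so a marker count may exist there. The FDR level is absent from Section 11.3, where the text is readable.

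A reader might infer that most markers at the targeted HR would be missed. The figures do not support this in general: at 50% incidence with 10 or 20 markers, more than half of the true markers are found even at FDR 5%. A reader might also infer a replacement detectable HR of about 0.73. That value holds only for FDR 5%, 10% true markers and 50% incidence, none of which the documents fix.

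**Conclusion.** The mismatch is established from Section 11.3 alone: the claim of over 80% power for HR 0.78 (0.75 for serial measurements) describes an unadjusted test of one prognostic marker and not the planned selection procedure. For a step-up procedure with an FDR level of 5% or less, power cannot be higher than the single-marker figure. How much lower it is depends on the FDR level, the number of markers, the fraction true and their correlation. With 10% true markers the illustration runs from about 46% to 75% at 50% incidence for FDR levels of 5% to 20%, and is about 28-41% at 25% incidence for FDR 5%. Lenient settings can preserve about 80%, so no single corrected figure follows from the documents. The Table 12 rows at 25% and 75% incidence are wrong independently of FDR: they are about 71-72% at the stated two-sided level, given 551 events, and 413 for the serial case by proportion. The point concerns exploratory analyses and has no bearing on the power for DFS or OS.

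**What to change.** In Section 11.3, label the power sentence and Table 12 as unadjusted, single-marker, prognostic power, and print the sidedness. Correct the rows at two-sided 5%: about 71-72% at 25% and 75% incidence and 83% at 50%, for HR 0.78 with 551 events and for HR 0.75 with about 413. Add that power under the planned FDR procedure will generally be lower. Give that power for a stated FDR level, number of markers and fraction true, either in the protocol or in the project plans required by Section 11.4, preferably by simulating the actual screening, LASSO and permutation steps. Any detectable HR should be printed together with those assumptions. The cost is a revised sentence and table with less favourable figures, plus a modest simulation. No patients, samples or procedures change.
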